Secondary end points	
 - Primary endpoint at 30 days,180 days and 2 years - All individual component of the primary endpoint at 30 days, 180 days, 1 year and 2 years: 
 -cardiac death -Myocardial Infarction (according to Third Universal Definition) -Stroke -Ischemia-driven target lesion revascularization (by PCI or CABG) - All revascularization (ischemia-driven and non-ischemia driven) at 30 days, 180 days, 1 year and 2 years: 
 -all target lesion revascularization (TLR) -all target vessel revascularization (TVR) -all non target vessel revascularization (non TVR) - complete revascularization at baseline procedure, anatomic and functional - Net benefit at 30 days, 180 days, 1 year and 2 years: association of composite events (all cause mortality, myocardial infarction, stroke, ischemia driven target lesion revascularization, and major bleedings). - Major bleeding complications (type 2, 3 and 5 BARC definition) at 30 days, 180 days,1 year and 2 years. (6) - Stent thrombosis according to the definition of ARC symptomatic or asymptomatic (definite + probable) at 30 days, 180 days, 1 year and 2 years. (5) - QoL, 12 months and 24 months - Depression scale at 12 months and 24 months - Cost effectiveness at 12 months
Pre-defined subgroup analyses	
 - Acute Coronary Syndrome vs non Acute Coronary Syndrome (stable angina and silent ischemia) - Patients \geq 85 years old - Women - Patients with type 2 diabetes mellitus

	- Patients with atrial fibrillation
Quality of life (QoL)	
Quality of life (QoL) will be assessed alongside the core clinical trial to evaluate the impact of the Synergy[®] II on a range of relevant quality of life (QoL) domains.
 
QoL and functional status will be assessed using a combination of generic and disease-specific measures selected to cover a broad range of health domains that may be affected by coronary artery disease, its treatment, and its complications. Mental health and depression will be assessed using the Geriatric Depression Scale. Health utilities will be assessed using the Euro QoL (EQ-5D 5L). These measures will be assessed using standardized, written questionnaires at baseline (prior to randomization), at 12 months and 24 months

Subject enrollment	A total of 1,200 subjects will be enrolled in approximately 40 international sites.

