First generations DES have been strongly criticized because of the small increased risk of late and very late stent thrombosis. Polymer hypersensitivity reactions, positive remodeling with late acquired malposition, delayed arterial healing, late stent fracture, and endothelial dysfunction are a few among the possible causes of the increased risk of very late stent thrombosis with first generations DES. The reduced rates of stent thrombosis with new generations of CoCr-EES stents may be attributed to the thromboresistant nature of the fluoropolymer or more rapid re-endothelialization, or both(3). Furthermore, an abluminal, fully biodegradable polymer-coated, thin struts DES, eluting everolimus such as the Synergy[®] II stent could therefore improve DES safety without reducing efficacy compared to BMS(4). In the recently published final 5-year report of the LEADERS (Limus Eluted From A Durable Versus ERodable Stent Coating) randomized, non inferiority trial, including 1,707 all comers patients, the biodegradable polymer-based DES (biolimus-eluting stents, BES) were compared to durable polymer DES (sirolimus eluting stents, SES). At 5 years, the BES was non-inferior to SES for the primary endpoint (186 [22.3%] vs. 216 [26.1%], rate ratio [RR]: 0.83 [95% confidence interval (CI): 0.68 to 1.02], p for non-inferiority <0.0001, p for superiority = 0.069); a composite of cardiac death, MI, or clinically indicated target vessel revascularization. Furthermore, BES was associated with a significant reduction in very late definite ST from 1 to 5 years (n = 5 [0.7%] vs. n = 19 [2.5%], RR: 0.26 [95% CI: 0.10 to 0.68], p = 0.003), corresponding to a significant reduction in ST-associated clinical events (primary endpoint) over the same time period (n = 3 of 749 vs. n = 14 of 738, RR: 0.20 [95% CI: 0.06 to 0.71], p = 0.005).

The ideal solution to reduce the unnecessary restenosis risk and the correlated rehospitalizations and the iatrogenic bleeding risk would be to treat patients ≥ 75 years with a DES and a short dual antiplatelet therapy similar to the one recommended with bare metal stents to conjugate the efficacy of newest DES and the safety of short duration of dual

antiplatelet therapy.

3-Study objective

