- **Primary endpoints** at 30 days, 180 days and 2 years
- **All individual component of the primary endpoint** at 30 days, 180 days, 1 year, and 2 years:
 - Cardiac death
 - Myocardial Infarction (according to Third Universal Definition)
 - Stroke
 - Ischemia-driven target lesion revascularization (by PCI or CABG)

-All revascularization (ischemia-driven and non-ischemia driven) at 30 days, 180 days, 1 year and 2 years:

- all target lesion revascularization (TLR)

- all target vessel revascularization (TVR)

- all non target vessel revascularization (non TVR)

-complete revascularization at baseline procedure, anatomic and functional

-Net benefit at 30 days, 180 days, 1 year and 2 years: association of composite events (all-cause mortality, myocardial infarction, stroke, ischemia driven target lesion revascularization, and **major bleedings**).

-Major bleeding complications (type 2, 3 and 5 BARC definition) at 30 days, 180 days, 1 year and 2 years (6)

-Stent thrombosis according to the definition of definite and probable stent thrombosis according to ARC (symptomatic or asymptomatic) at 30 days, 180 days, 1 year and 2 years (5),

-QoL at 12 months and 24 months

-Depression scale at 12 months and 24 months

-Cost effectiveness at 12 months

6-Selection and withdrawal of the subjects

6-1 Subject population

Male and female subjects could be enrolled in the present study if they are 75 years old or older at the time of randomization. The randomized trial will enroll approximately 1,200 patients who need to meet ALL eligibility criteria and provide written informed consent prior to randomization. Each site should enroll a minimum of one randomized subject, and may not enroll more than a maximum of 120 randomized subjects.

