Antithrombotic regimen within the cathlab, including unfractionated heparin, low molecular weight heparin, bivalirudin, fondaparinux, is left to the physician discretion. GpIIb / IIIa inhibitors can be used in selected cases in patients with STEMI but are not recommended for stable patients or for patients with silent ischemia.

-Dual antiplatelet therapy will be administered for **similar duration** after Synergy[®] II and Omega[®]/Rebel[®] stent or any other BMS available implantation. DAPT duration will be one month after PCI for stable angina and silent ischemia, and six months after PCI for acute coronary syndroms, **irrespective of the type of stent** (Synergy[®] II or Omega[®]/Rebel[®] stent).

-Aspirin will be prescribed to all patients at an initial intra venous or oral loading dose of 150-300mg and at a maintenance dose of 75-100 mg orally daily, indefinitely (except in patients with chronic anticoagulation). For patients not already on P2Y₁₂ inhibitors they will be added to aspirin before or immediately after percutaneous coronary intervention and maintained over one month (stable angina or silent ischemia) or 6 months (ACS).

-All patients in the trial will be treated by either:

-clopidogrel 600mg loading dose and 150mg/d or 75mg/d

OR

-prasugrel 60mg loading dose and 5 mg/d orally

OR

-ticagrelor 180mg loading dose and 90mg/bd orally

over one month after PCI. The P2Y₁₂ inhibitor will be prolonged over 6 months only in patients with acute coronary syndrome, irrespective of the type of the stent.

Optimal medical treatment.

Anti ischemic treatment should be added to medical treatment and include beta blocker agents in patients without contra indication.

Calcium channel blocking agents can replace beta blocker agents in patients with contra indications to these agents.

A proton pump inhibitor (PPI) is strongly recommended according to physician discretion (pantaprazole 20mg, ezoprazol 20mg, lanzoprazole 20mg, rabeprazole 20mg or omeprazole 20mg).

10-Follow-up visits

Every effort should be made for collecting the subject data thanks to an on-site visit or telephone contact, as described below:

- 30 days(+/- 5 days) visit: office visit

-
- 180 (+/-2 weeks): telephone contact or office visit
 - 1 year visit (+ 4 weeks): office visit
 - 2 years (+/-4 weeks) visit: telephone contact or office visit.

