Type 5a : Probable fatal bleeding ; no autopsy or imaging confirmation but clinically suspicious

Type 5b : Definite fatal bleeding ; overt bleeding or autopsy or imaging confirmation

Major Arrhythmia

Ventricular tachycardia or fibrillation requiring cardioversion or countershock; atrial fibrillation lasting >24 hours; bradycardia or conduction system disease requiring a permanent pacemaker.

Renal Failure

Serum creatinine increase by ≥ 1 mg/dL or need for dialysis.

Stent Thrombosis

For this trial, stent thrombosis will be defined as the occurrence of definite stent thrombosis according to the ARC criteria.

1. Stent Thrombosis: Timing

Type Timing(5)

Acute stent thrombosis: 0 to 24 hours after stent implantation

Subacute stent thrombosis > 24 hours to 30 days after stent implantation

Early stent thrombosis (0 to 30 days)

Late stent thrombosis† > 30 days to 1 year after stent implantation

Very late stent thrombosis† > 1 year after stent implantation

Stent thrombosis will be reported as a cumulative value over time and at the various individual time points specified above (except very late thrombosis for an endpoint related reason). Time 0 is defined as the time point after the guiding catheter has been removed and the subject has left the catheterization laboratory.

†Includes primary as well as secondary late stent thrombosis; secondary late stent thrombosis is a stent thrombosis after a target lesion revascularization.

2. ARC Definitions of Definite, Probable, and Possible Stent Thrombosis (5)

□ **Definite Stent Thrombosis**

Definite stent thrombosis is considered to have occurred by *either* angiographic or pathological confirmation:

a. Angiographic confirmation of stent thrombosis†

The presence of a thrombus‡ that originates in the stent or in the segment 5 mm proximal or distal to the stent and presence of at least 1 of the following criteria within a 48-hour time window:

1. Acute onset of ischemic symptoms at rest
2. New ischemic ECG changes that suggest acute ischemia
3. Typical rise and fall in cardiac biomarkers (refer to definition of spontaneous MI: Troponin or CK-MB > 99th percentile of URL)

4. Non occlusive thrombus

a. Intracoronary thrombus is defined as a (spheric, ovoid, or irregular) non calcified filling defect or lucency surrounded by contrast material (on 3 sides or within a coronary stenosis) seen in multiple projections, or persistence of contrast material within the lumen, or a visible

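### Stent thrombosis at 2 years is a secondary endpoint, but the appendix excepts very late thrombosis from reporting and section 13.2 stops event collection at the 12-month visit

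*Protocol*

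**What the plan says.** The endpoint lists are unqualified. The Protocol Summary gives stent thrombosis as "symptomatic or asymptomatic (definite + probable) at 30 days, 180 days, 1 year and 2 years. (5", and section 5-2 repeats it for definite and probable events, "according to ARC (symptomatic or asymptomatic) at 30 days, 180 days, 1 year and 2 years". Sections 4-2 and 10 plan the contact that would supply the last value: "2 years (+/-4 weeks) visit: telephone contact or office visit". Section 10 also has the follow-up visits record adverse events, including MACCEs.

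Two other places point the other way.

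- **Section 19-1-4, Stent Thrombosis, Timing.** Very late thrombosis is "> 1 year after stent implantation". The reporting rule reads "Stent thrombosis will be reported as a cumulative value over time and at the various individual time points specified above", followed in parentheses by "except very late thrombosis for an endpoint related reason". The phrase about an endpoint-related reason is not explained.
- **Section 13.2.** Endpoint-related events, serious or not, are collected in the eCRF from PCI to the 12-month visit. Nothing is said about collection after that visit.

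Section 4-1 also gives follow-up as 1 year, while section 4-2 goes on to 2 years.

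**The concern.** Every stent thrombosis that could separate a 2-year value from a 1-year value occurs more than 1 year after implantation, and so is very late by the protocol's own definition. An exception for very late thrombosis therefore removes exactly what the 2-year time point is there to add. A reader of the results would see a 2-year figure and take it to cover the second year.

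This is more than detail left to the statistical analysis plan, because the protocol states rules that cannot all be followed. A site or events committee that follows sections 13.2 and 19-1-4 would leave year-2 events out; one that follows section 5-2 would count them. A later analysis plan can choose between reporting rules, but it cannot recover events that were not collected or adjudicated.

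The topic matters to the protocol's own argument. Section 2 says: "First generations DES have been strongly criticized because of the small increased risk of late and very late stent thrombosis". It then cites fewer very late events with a biodegradable polymer in support of this type of stent.

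**Working it through.** **Step 1: the texts side by side.** Let N1 be the number of stent thromboses up to 1 year and V the number from more than 1 year to 2 years. A 2-year cumulative value should be N1 + V.

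- *Plain reading of 19-1-4.* The exception applies to the whole sentence. All of V is very late, so reported V = 0 and the reported 2-year value is N1 + 0 = N1, the same as the 1-year value.
- *Narrower reading of 19-1-4.* The exception applies only to the separate time windows. The cumulative 2-year value is still N1 + V, and only the separate very late line is dropped. V must still be collected, however, and section 13.2 ends collection at the 12-month visit. That visit may be up to 4 weeks late (sections 4-2 and 10), so at most the first few weeks of V would be caught if section 13.2 were followed literally.

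The 2-year endpoint in section 5-2 is secured under neither reading.

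**Step 2: how many events.** The protocol gives no expected stent thrombosis rate for its own arms. The only very late figures are in section 2, from the 5-year report of a randomised comparison of a biodegradable-polymer biolimus stent with a durable-polymer sirolimus stent: 0.7% and 2.5% definite events from year 1 to year 5. Two assumptions are needed: a constant rate over those 4 years, and 70% to 100% of the 600 patients per arm still at risk after year 1 (420 to 600).

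Annual risk = 1 − (1 − r)^(1/4); expected events = annual risk × number at risk.

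- r = 0.7%: 1 − 0.993^0.25 = 0.175% a year; × 420 = 0.7 and × 600 = 1.1 events per arm.
- r = 2.5%: 1 − 0.975^0.25 = 0.631% a year; × 420 = 2.7 and × 600 = 3.8 events per arm.

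The range is about 1 to 4 events per arm in year 2.

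**Step 3: could those events support a comparison?** If the two arms differed as much as those two stents did (0.631% against 0.175% in year 2, 600 per arm, two-sided 0.05), power would be about 24%. This is a rough normal approximation at such small counts. The year-2 data are descriptive.

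**Step 4: the sample size.** The 560 per arm in section 12 rests on the 1-year primary endpoint and uses no stent thrombosis rate. It reproduces. With 31% against 0.75 × 31% = 23.25%, exponential events and dropout reaching 15% at 1 year, the variance per patient of each Kaplan-Meier rate is S²λ(e^(λ+γ) − 1)/(λ+γ), where S is the 1-year event-free proportion, λ = −ln S and γ = −ln 0.85. This gives 0.2334 and 0.1945. Then n = (0.2334 + 0.1945) × (1.960 + 0.842)² / 0.0775² ≈ 559 per arm. Nothing in this point changes that figure.

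**The case against.** The strongest reply is grammatical. The parenthesis directly follows the mention of individual time points and may qualify only that item, which leaves the cumulative 2-year value intact. Other parts of 19-1-4 fit this: probable thrombosis based on MI has no time limit, and possible thrombosis runs to the end of follow-up. This stands as a fair alternative, so it cannot be said that year-2 events are certain to be lost. It does not remove the ambiguity, and it does not touch section 13.2.

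Three stronger readings are tempting and are not supported.

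- *That the trial cannot meet its safety objective.* The Protocol Summary specifies safety as a similar risk of major bleeding, at a median follow-up of about one year. Section 3 also ties the primary objective to one year. Very late thrombosis is named in neither.
- *That very late thrombosis is the reason for choosing this stent.* Section 2 makes that criticism of first-generation drug eluting stents and calls newer ones effective and safe. Its closing rationale is less restenosis and less bleeding, through a drug eluting stent with short dual antiplatelet therapy. The very late thrombosis data are one supporting argument. They compare two drug eluting stents that are not arms of this trial, and no bare metal stent.
- *That a late excess or benefit would be hidden altogether.* With 1 to 4 events per arm, the comparison could hardly show either. MI from stent thrombosis also counts as MI under 19-1-2, and MI and ischemia-driven target lesion revascularization are reported at 2 years. Symptomatic cases would therefore largely stay visible there, provided that the 2-year contact records them as section 10 foresees. Section 13.2, read literally, puts that in doubt as well.

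**Conclusion.** The contradiction is real and should be corrected, but it is limited. If the rules in 19-1-4 and 13.2 are followed as written, the 2-year value of a listed secondary endpoint omits the second year. If the exception is read narrowly, the endpoint is ambiguous and its data collection is not provided for in section 13.2. About 1 event per arm is at stake at the 0.7% rate and up to about 4 at the 2.5% rate. Those counts rest on a constant rate over years 1 to 5 and on borrowed figures, so they indicate scale only. The consequence is an inaccurate safety description under a 2-year label, with no effect on power, the primary endpoint or the primary objective.

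The statement in 19-1-4 that thrombosis means definite events, against definite and probable in the endpoint lists, is a separate mismatch and plays no part here.

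**What to change.** Make three linked changes.

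1. In 19-1-4, delete the parenthesis "except very late thrombosis for an endpoint related reason".
2. In 13.2, extend eCRF collection of endpoint-related events to the 2-year contact, and bring the 1-year follow-up statement in 4-1 into line with 4-2. Deleting the parenthesis alone would not be enough.
3. State that adjudicated stent thrombosis is reported cumulatively to 2 years, and separately for more than 1 year to 2 years.

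If the sponsor does not intend to collect these events, the alternative is to remove the 2-year time point for stent thrombosis from the Protocol Summary and section 5-2. That settles this endpoint only, since section 13.2 would still conflict with the other clinical endpoints listed at 2 years.

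The cost of the first option is small: a few sentences of text, and collection and adjudication of a few extra events at a contact that is already planned.

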The authors shared full access to the total data in the study and had final responsibility for the submission for publication.

*One of the following regimen

22. Medico-economic study

Medico economic evaluation of the SENIOR study:

The Elderly population is at higher risk of bleeding than the younger one and for this reason often receive bare metal stents (BMS) to avoid to be exposed of the risk of bleeding of the 6 months to one year treatment with dual antiplatelet required by the drug eluting stents (DES). A new generation of DES (Synergy, BSCI) seems to allow more rapid healing of the artery thanks to a rapid bioabsorbable coating) and permits an antiplatelet treatment as short as the one of a BMS; if so it provides the advantage of reducing restenosis rate like a DES being as safe as a BMS.

The SENIOR trial compares the BMS Omega[®]/Rebel[®] to the DES Synergy[®] II in a population older than 75.

The initial hospital costs of treating the patients should be the same, except the price of the DES which is superior to the BMS one. During the one year follow up, the potential costs associated to bleeding should be the same in the two groups as they receive the same antiplatelet treatment, but it is expected that the group receiving the DES should have less rehospitalisation for re-intervention and this should at least counterbalance the initial difference in the costs of the stents.

Economic evaluation

An economic evaluation along the SENIOR trial in the context of the healthcare systems in participating counties is performed. The incremental cost-effectiveness ratio (i.e. the net incremental cost of PCI treatment with the Synergy[®] II stent over the one of the Omega[®]/Rebel[®] stent divided by the net incremental health outcomes of each strategy) will be estimated. The time horizon is 1 year (i.e. the duration of follow-up). The perspectives chosen

for the economic analyses are: 1) the payer (National Health Service or Social Health Insurance) and 2) the hospital.

Analyses will be performed using direct medical costs. Given the time horizon, no discounting is required. The primary analysis will be a cost-effectiveness analysis. Effectiveness will be majored by the incidence of MACCE.

We do not account for indirect costs or for nonmedical costs. A secondary analysis will compare QALYs and an estimated cost-utility ratio.

Costs

Costs for each strategy include:

- the initial procedural costs for patients in the PCI+ DES arm
- the initial procedural cost for patients in the PCI+ BMS arm
- costs during the 1-year follow-up for all patients.

Per diem costs of CCU and ward admission will be added to procedure costs.

In order to limit data collection costs we propose to perform microcosting on a voluntary basis in centers where computerized information on resource utilization and costs is available.

Index procedure

Cost of the index procedure for patients randomized in the PCI + DES and PCI + BMS arm will be estimated from the latest DRG schedule at the date of the study completion in countries where DRGs are used and from the hospitals' billing in other countries. Physicians' fees will be added whenever relevant.

Follow up

Hospital costs

Costs of repeat PCI without MI, repeat PCI, MI, coronary artery bypass grafting, other adverse events are based on payer's reimbursement rate per diagnosis-related group.

Costs of admission in rehabilitation hospitals are also considered. The total number of days in rehabilitation centers is recorded on the CRF.

The national average reimbursement rate for each of DRG is publicly available. DRG information for each event is obtained either directly from the participating hospital's information system or by allocating DRGs from the diagnosis and procedure codes collected in the CRF. For rehabilitation centers the cost of admission is estimated either by a specific DRG or by a per diem, depending on the country.

Health Outcomes

QALYs are derived from health-related quality of life (EQ-5D -5 L) and MACCE and survival during the 1-year time horizon of the trial. Quality-of-life indexes (utilities) were evaluated at baseline, after 1 year and after 2 years using the EuroQuol 5 dimension health survey with weights from the participating countries where these weights are available (UK, Germany, France...). (8)

The overall QALYs are estimated as the area under the curve determined by these 3 values. Missing data are replaced with estimates using bootstrap resampling within the respective study arm.

Results of the economic evaluation are be presented in incremental cost effectiveness (MACE averted) and cost utility ratios (additional cost per additional QALY) (9-10)

Statistical Analysis

Categorical data are reported as frequencies, and continuous data are given as mean \pm SD. Categorical data are compared by use of the χ^2 test. Continuous data (costs and QALYs) are compared by use of the Student *t* test. We report 95% confidence intervals when appropriate. Confidence intervals for both differences in QALYs and costs are estimated by the bootstrap

technique using the percentile method and 5000 replications. A 2-sided value of $P < 0.05$ is considered to indicate statistical significance.

An analysis of resource utilization can be performed by pooling data from participating centers. The analysis of costs requires a different approach because of differences in unit prices for labor and DRGs. We propose 2 different analyses, 1) an analysis per country, using the country-specific unit costs and resource utilization for the sub population of patients recruited in the country. This analysis can be performed only in countries with a large recruitment; 2) a pooled analysis with standardization of unit costs on country specific costs, for each country in turn. (9)

Sensitivity analyses are performed for a range of $\pm 10\%$ on all prices and for $\pm 10\%$ on utilities. All analyses are performed with the use of STATA (StataCorp, 2009).
